5.2 Clinical/Laboratory Criteria

- _____ a. Patients must be post-menopausal, as defined by at least one of the following:
 - 1. ≥ 12 months since the last menstrual period OR
 - 2. prior bilateral oophorectomy OR
 - 3. previous hysterectomy with one or both ovaries left in place (or previous hysterectomy in which documentation of bilateral oophorectomy is unavailable) AND (unless ≥ 60 years of age) FSH values consistent with the institutional normal values for the post menopausal state OR
 - 4. have been on LHRH agonist therapy for at least 3 months and estradiol levels drawn within 28 days prior to registration are consistent with the institutional normal values for post-menopausal state.
- _____ b. Patients must currently be taking one of the following aromatase inhibitor (AI) doses for at least 21 days prior to registration and plans to continue for at least an additional 180 days after registration. Patients may have received any number of prior AI therapies, but the first AI therapy must have started no more than 36 months prior to registration.
 - 1. anastrozole (Arimidex®) 1 mg daily
 - 2. letrozole (Femara®) 2.5 mg daily
 - 3. exemestane (Aromasin®) 25 mg daily

SWOG Patient No. _____

Patient's Initials (L, F, M) _____

- _____ c. Patients must have aromatase inhibitor (AI) associated musculoskeletal symptoms that began or increased after starting AI therapy. New musculoskeletal pain must not be due specifically to fracture or traumatic injury.
- _____ d. Patients must have completed the **S1202** Brief Pain Inventory-Short Form (BPI-SF) within 7 days prior to registration. Patients must have an "average pain" of at least 4 on the BPI-SF (item #4).
- _____ e. Patients must have Zubrod performance status of 0-2 (see [Section 10.3](#)).
- _____ f. Patients must have no known allergy or hypersensitivity to duloxetine or any of the inactive ingredients in the matching placebo.
- _____ g. Patients must not have any contraindicated concurrent illnesses listed on the duloxetine package insert including:
- Current primary psychiatric diagnosis (schizophrenia, psychosis) or suicidal ideation, history or bipolar disorder, or seizure disorder
 - History of alcohol or other substance abuse or dependence within 365 days prior to registration.
 - Chronic liver disease
 - End stage renal disease
 - Uncontrolled narrow-angle glaucoma
 - Clinically significant coagulation disorder

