6.0 STRATIFICATION FACTORS

Patient randomization will be dynamically balanced according to the following stratification factors: baseline pain score (BPI-SF item #4) (4-6 vs 7-10); and prior taxane use (yes vs. no).

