11.0 STATISTICAL CONSIDERATIONS

11.1 Primary Objective

Joint pain will be assessed using “average pain” according to the BPI-SF. Enrollees must currently be taking AIs and must exhibit joint pain with a minimum BPI-SF average pain score of 4; scores of 4 to 10 are considered to reflect moderate to severe pain. (42) Patients will be stratified at randomization by the use of average baseline pain according to the BPI (4-6 vs 7-10) and prior taxane use (yes vs. no). The primary assessment time of 12 weeks, upon which power calculations are based, corresponds to completion of the intervention and allows cross-trial comparisons to be made with **S0927**, which is evaluating a different pharmacologic agent for treatment of AIMSS in the same patient population.

This study stipulates an $\alpha=0.05$ two-sided test, with an estimated 5% non-adherence (reducing the nominal effect size) and 15% dropout rate (increasing the total required sample size) at 12 weeks after randomization. (16, 43) In addition, the design will

incorporate a 10% contamination rate (which also reduces the nominal effect size) based on the assumption that a portion of the patients will not benefit from intervention based on joint pain with a different etiology that is not associated with AI treatment (this has a similar impact on power calculations as a “drop-in” rate).[\(44\)](#)

The proposed sample size incorporates adjustments for loss, non-adherence, and contamination. The power for the design will be a function of the difference detected and the standard deviation at 12 weeks after randomization.

Difference Detected: Although a difference of 2 points in the BPI has been identified as representing a clinically meaningful *individual* level difference, for power calculations assessing group-level differences, we will test a smaller effect. [\(45\)](#) Specifically, an incremental difference in pain reduction due to duloxetine over placebo of about 1.0 points at 12 weeks has been repeatedly found in the setting of fibromyalgia. [\(43,46\)](#)

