Standard Deviation: Multiple studies of AI-induced joint pain have found the standard deviation for BPI “average pain” at follow-up on placebo to be about 2.0 to 2.5 points. [\(47,8\)](#) The design assumes a common standard deviation between arms; a similar standard deviation has been observed in a pilot study of duloxetine. [\(16\)](#) We assume a SD of 2.3 points at 12 weeks for this study (the estimated average SD found in Arnold, Clin J Pain, 2009). [\(8\)](#)

For a 1.0 point difference and a 2.3 point SD at 12 weeks, with other parameters as specified above, 270 eligible patients would be required for 80% power under a two-arm normal design. Power will be higher with lower observed standard deviation or a larger observed difference.

The following considerations clarify the impacts of loss, non-adherence, and contamination on the sample size calculations:

- A two-arm normal design with $\alpha=0.05$ two-sided test and a 2.3 point SD to detect a difference of 1.0 points requires approximately 166 patients (83 per arm) for 80% power.
- An estimated 5% non-adherence and 10% contamination both reduce the nominal effect size, from 1.0 points to 0.85 points. This increases the required sample size to 230 total patients (115 per arm).
- To account for an estimated 15% dropout rate, the total required sample size must be further increased by 15%, as in $230/0.85 = 270$ total patients.

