The primary analysis will rely on longitudinal measures of BPI at Weeks 2, 6, and 12 for improved power. (Thus the proportion of patients with zero follow-up observations will likely be less than the specified 5% non-adherence and 15% dropout at 12 weeks used for power calculations.) Assessment windows of +/- 7 days, +/- 14 days, and +/- 14 days will be allowed for the 2, 6, and 12 week timepoints. (Given the primary analysis is based on longitudinal measures, a sensitivity analysis will consider all observations within 14 weeks of registration.) The analysis will be performed using mixed models, adjusted for baseline average pain and the stratification factors. To minimize missed assessments, SWOG utilizes an electronic system to remind institutions in real-time that patients are due for follow-up assessment. If the proportion of missing follow-up data is >20% (the sum of the specified targets for non-adherence and dropout), plots of mean pain levels over time for patients grouped by number of follow-up responses will be examined to check for patterns of informative missing data. Should these plots suggest that data may not be missing at random, pattern mixture models, which models missingness patterns through stratification, will be utilized for analysis of the longitudinal BPI pain data. [\(48, 49\)](#)

Under the intention-to-treat principle, the primary analysis will be based on all eligible, randomized patients. To allow for an ineligibility rate of 8%, as found on our recent Symptom Control study [S0715](#), a total of 294 patients will be enrolled to achieve 270 eligible patients.

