11.3 Secondary Endpoints

The following secondary analyses will be conducted:

- a. Multiple linear regression analyses of the individual assessment timepoints will be conducted to identify potential critical effectiveness timepoints and to allow comparisons to other studies. These analyses will include the baseline score (as a covariate) as well as the pre-specified stratification factors.
- b. At weeks 2, 6, and 12, we will investigate whether duloxetine 60 mg daily:
 1. Decreases worst joint pain according to the BPI.
 2. Improves functioning, pain, and stiffness in the knees/hips according to the Western Ontario and McMaster Universities Osteoarthritis (WOMAC) scale. Differences between the two study arms of at least two points on the WOMAC Index are of interest. [\(50, 51\)](#) We will also evaluate clinically meaningful change for the WOMAC Index with respect to the $\frac{1}{3}$ to $\frac{1}{2}$ standard deviation during the study period of 12 weeks.
 3. Improves function, pain and stiffness in the hands according to the Modified Score for the Assessment and Quantification of Chronic Rheumatoid Affections of the Hands (M-SACRAH). Differences between the two study arms of at least two points on the M-SACRAH are of interest. [\(50,51\)](#) We will also evaluate clinically meaningful change for the M-SACRAH with respect to the $\frac{1}{3}$ to $\frac{1}{2}$ standard deviation during the study period of 12 weeks.
 4. Improves functional quality of life as measured by the Functional Assessment of Cancer Therapy-Endocrine Scale (FACT-ES).[\(52,53\)](#) Trial Outcome Index (TOI). Clinically meaningful change in FACT-ES TOI scores will also be based on $\frac{1}{3}$ to $\frac{1}{2}$ of a standard deviation. [\(53-55\)](#)
 5. Improves the proportion of patients reporting changes for the better versus worst as measured by the Global Rating of Change Scale. The GRCs for joint pain and for joint stiffness will be used to identify patients who report they are worse (combining scores of -1 through -3), the same score (score of 0), or better (combining scores of +1 through +3) since the last time they completed the questionnaire. [\(54-56\)](#) Mean scores for the WOMAC Index, BPI, M-SACRAH, and FACT-ES TOI will be compared for groups based on those patients who select “a little better” and “a little worse” on the GRC ratings to identify minimally important change. [\(54-56\)](#)

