6. Reduces depression as measured by the Patient Health Questionnaire (PHQ-9). Differences between the two arms of at least five points on the PHQ-9 at 12 weeks will be of interest. (57) Clinically meaningful change in PHQ-9 scores will also be based on $\frac{1}{3}$ to $\frac{1}{2}$ of a standard deviation. (57)
 7. Decreases analgesic use.
 8. Increases adherence to, and reduces the discontinuation rate for, AI therapy.
 9. Affects measures of pain interference.
 10. Reasons for treatment discontinuation will also be described.
- c. Interaction tests between treatment and stratification variables will be conducted to explore whether these factors are predictive of average pain scores.
 - d. A logistic regression analysis of responders will be conducted, where a response to intervention is defined as a reduction of 2 or more points in average pain according to the BPI. (50)
 - e. In addition, we will explore the relationship between the severity of arthralgias and degree of benefit from therapy in each of the treatment groups and inherited variants in genes responsible for duloxetine metabolism and activity (COMT, HTR3A, SLC6A2, SLC6A4, CYP1A2, CYP2D6) and aromatase (CYP19A1). Finally, we will explore the relationship between baseline and change in serum inflammatory cytokine levels with 12 weeks of treatment and the degree of benefit from therapy in each of the treatment groups.

For linear scales, secondary endpoints will be analyzed using multiple linear regression analyses including the baseline score as a covariate and the pre-specified stratification factors. For binary outcomes, logistic regression will be used.

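### Section 11.3c tests treatment by baseline pain only on the 4-6 vs 7-10 split; if benefit changes roughly linearly with baseline pain, this loses about 25-47% of the information for that exploratory test

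*Combined protocol and SAP*

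**What the plan says.** Section 11.3, item c, of the combined protocol and SAP plans the following: "Interaction tests between treatment and stratification variables will be conducted to explore whether these factors are predictive of average pain scores". It gives no coding, effect size or power for these tests.

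The pain variable is defined in two places, both times with two levels. Section 6.0 lists "baseline pain score (BPI-SF item #4) (4-6 vs 7-10") and Section 11.1 has patients "stratified at randomization by the use of average baseline pain according to the BPI (4-6 vs 7-10").

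The full score is also in hand. Section 5.2d requires a pre-registration average pain "of at least 4 on the BPI-SF (item #4"). The plan treats score and stratum as separate terms: the primary mixed model is "adjusted for baseline average pain and the stratification factors", and item a of Section 11.3 says "These analyses will include the baseline score (as a covariate) as well as the pre-specified stratification factors". No section plans an interaction of treatment with the score itself. Item e of Section 11.3 concerns genetic variants and cytokines.

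**The concern.** Stratifying randomisation on a split does not oblige the analyst to test effect modification on that split. If benefit rises or falls steadily with baseline pain, a two-level version treats a score of 4 like a 6 and a 7 like a 10, and so discards part of the signal. The split is also likely to be unbalanced: at the pilot's baseline mean and SD, only about 18% of patients would score 7-10.

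The trial is sized for a main effect, so any interaction test starts weak. A severity gradient could be missed more often than the collected data require. What is at stake is confined to this exploratory question.

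**Working it through.** **Inputs from the documents.** Two-sided alpha 0.05, power 80%, SD 2.3, difference 1.0 diluted to 0.85, 15% dropout, 8% ineligibility (Section 11.1). Baseline average pain in the pilot: mean 5.5, SD 1.1, n = 29 (Section 2.0, Table 1), also with entry at 4 or more. The documents give no other baseline distribution.

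**Assumptions.** Whole-number scores 4-10; a discretised normal shape; equal arms; the slopes and step used below.

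**1. The plan's own sample size.** Per arm, n = 2(1.96 + 0.842)² × 2.3² / d².
- d = 1.0: 83.0 per arm, 166 in total.
- d = 0.85: 83.0 / 0.7225 = 114.9, so 115 per arm and 230 in total.
- 230 / 0.85 = 270.6; 270 / 0.92 = 293.5.

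The stated 166, 230, 270 and 294 all reproduce. No figure is stated for the interaction test.

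**2. Information kept by the split.** When the effect is linear in the score, the efficiency of the split relative to the score is their squared correlation: cov² / [var(score) × q(1 − q)], with q the share scoring 7-10.
- Pilot mean and SD matched exactly: q = 0.181, cov = 0.318, var = 1.21. Efficiency = 0.101 / (1.21 × 0.148) = 0.56, a **44% loss**. The split needs 1 / 0.564 = 1.77 times the patients.
- Means of 5.25-6.0 with SDs of 1.1-1.4: loss 31-47%. At SD 1.5 it is 30%.
- Flat over 4-10: var = 4, q = 4/7, cov = 6/7. Efficiency = (36/49) / (4 × 12/49) = 0.75, a **25% loss**.

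Shape matters as well. A small set of 18 random single-peaked distributions close to the pilot's mean and SD gave losses of 21-48%, so 25-47% is a working range and not a bound.

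**3. Power if the effect is linear.** With N = 230, SD 2.3 and the pilot spread, the standard error of the interaction slope is 2 × 2.3 / (√230 × 1.1) = 0.276. For slope b, z = b / 0.276 on the score and z × √0.564 on the split.

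| Assumed slope per point | Score: z, power | Split: z, power |
|---|---|---|
| 0.2 | 0.73, 11% | 0.54, 9% |
| 0.3 | 1.09, 19% | 0.82, 13% |
| 0.5 | 1.81, 44% | 1.36, 27% |
| 0.77 | 2.80, 80% | 2.10, 56% |

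Simulation with arm, score, stratum and taxane in the model gives slightly lower figures: about 42% vs 24% at slope 0.5, about 11-16% vs 7-10% at slopes 0.2-0.3, and 79% vs 54% at 0.77.

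**4. Power if the effect steps at 7.** For an assumed 1.5-point step, the split has z = 1.5 × √0.148 × √230 / 4.6 = 1.90, power 48%. The linear term picks up a slope of 1.5 × 0.318 / 1.21 = 0.39, so z = 1.43 and power 30%. Simulation gives 47% and 29%. The ranking reverses.

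**The case against.** The strongest reply is that nothing in item c is an error. Testing the factors used at randomisation, at pre-defined cut-points, is a standard choice. The text says it explores those factors and does not promise a severity-response curve. That stands, and it makes this an improvement rather than a correction.

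The second reply is that the loss is conditional. A reader might infer that the split throws away a third to a half of the information whatever the truth. The documents do not support that: they say nothing on the form of effect modification, and step 4 shows the linear term losing by the same factor if the effect steps at 7. Equally, no passage argues for a step at 7; Section 11.1 groups 4 to 10 together as moderate to severe pain. Neither form can be presumed, so the score should be added and the split kept.

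The third reply is that a slope of 0.5 is large. It implies benefit differing by 3 points between scores 4 and 10, against a planned average effect of 1.0. This also stands. At slopes of 0.2-0.3 the gain is only a few percentage points of power, and a null result stays uninformative under either coding.

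A reader might also expect a null test to be reported as equal benefit at all pain levels. No passage says so, and no decision rule hangs on the test. It is a risk to guard against with one sentence.

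**Conclusion.** The point holds in conditional form. As written, item c tests modification by baseline pain only on the two-level stratum, although the 4-10 score is collected on everyone and already modelled. If modification is roughly linear, that loses about 25-47% of the information for the test, and 44% at the pilot's mean and SD. The size rests on linearity, on a pilot of 29 patients and on an assumed shape for the baseline scores; this trial's own baseline spread is not in the documents.

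A reader might infer that the primary result or the design is compromised. It is not: the primary analysis, its type I error and the sample size are unaffected, and the test is exploratory. This is a cheap, low-priority improvement.

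**What to change.** In Section 11.3, item c:
- Pre-specify treatment by centred continuous baseline average pain, in the model that already carries the score, as the test of effect modification by severity.
- Keep the planned 4-6 vs 7-10 interaction beside it, with the treatment effect and 95% CI in each stratum, as a check on linearity.
- State that a non-significant interaction is not evidence of equal benefit across pain levels.
- Leave the taxane interaction unchanged; that factor is binary.

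The cost is one model term on data already collected. The downside is one extra exploratory test and a linearity assumption, which the stratum results help to check. Naming the lead test in advance also removes a later choice between score and split.

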Safety was assessed in all 34 patients who received at least one dose of study medication. Adverse events and treatment discontinuation rates were similar to previously reported duloxetine studies (10,11,19,20) Seven patients (20.6%) discontinued therapy due to adverse events. The majority of subjects who discontinued therapy because of adverse events did so within a few days of starting treatment. Reasons for treatment discontinuation included Grade 1 and/or 2 drowsiness, headache, and nausea. The majority of reported adverse events were Grade 1 and/or 2 fatigue and drowsiness, nausea, xerostomia, constipation, and headache, consistent with prior studies of duloxetine, and 76.5% of patients reported at least one adverse event. The only Grade 3 or 4 adverse event reported was tachycardia, thought by the treating physician to be unlikely related to treatment. Since AI therapy acts by suppressing estradiol production, the impact of duloxetine therapy on serum estradiol concentration was assessed. Duloxetine therapy did not affect serum estradiol concentrations in the 23 subjects who completed 8 weeks of treatment.

Table 1. Change in outcome measures with duloxetine therapy (n=29).						
Outcome measure	Baseline	2 weeks	4 weeks	6 weeks	8 weeks	P value ²
Average pain (0-10)	5.5 (1.1) ¹	2.5 (1.5)	2.1 (2.0)	2.3 (1.8)	2.1 (1.6)	<0.0001
Worst pain (0-10)	7.2 (1.4)	3.4 (2.4)	3.1 (2.6)	3.3 (2.0)	2.9 (2.3)	<0.0001
Pain interference (0-10)	4.3 (2.0)	1.6 (1.7)	1.3 (1.7)	1.1 (1.0)	1.0 (1.3)	<0.0001
HAQ (0-3)	0.48 (0.31)	0.20 (0.26)	0.25 (0.33)	0.21 (0.29)	0.23 (0.28)	0.001
Hot flash interference (0-100; HFRDIS)	17.1 (21.9)		10.1 (14.5)		7.0 (12.5)	0.02
Hot flash interference (1-8; MENQOL vasomotor subscale)	2.9 (2.0)		2.2 (1.4)		2.6 (1.7)	0.31
Depression (CESD)	10.1 (8.8)		5.8 (4.7)		3.5 (3.2)	0.004
Sleep (0-21)	8.0 (3.3)		7.8 (4.1)		6.9 (4.0)	0.03
¹ Baseline to 8 weeks columns show mean score (SD)						
² Comparison between baseline and 8 weeks						

Correlative studies.

Identification of patients who are more likely to respond to duloxetine therapy prior to treatment initiation could impact management of AIMSS and could yield additional information regarding the mechanism underlying development of AIMSS. Potential approaches for identifying predictive markers of response to therapy include evaluation of associations with inherited genetic variants in candidate genes and with baseline or change in circulating inflammatory markers.

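### Section 11.3e specifies no marker-by-treatment contrast, so as written it does not separate markers that modify the duloxetine effect from markers that track pain change in either arm

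*Combined protocol and SAP*

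**What the plan says.** The correlative-studies part of Section 2.0 opens with the purpose: "Identification of patients who are more likely to respond to duloxetine therapy prior to treatment initiation could impact management of AIMSS". It then says how this might be done: "Potential approaches for identifying predictive markers of response to therapy include evaluation of associations with inherited genetic variants in candidate genes", and adds baseline or change in circulating inflammatory markers. The same section also hopes to learn about the mechanism of AIMSS, and it labels the correlative work exploratory and hypothesis-generating.

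The objectives in Section 1.3 are narrower. Objective k relates inherited variants to change in pain over 12 weeks. Objective l concerns the effect of treatment on serum cytokines.

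The analysis is in Section 11.3e. For COMT, HTR3A, SLC6A2, SLC6A4, CYP1A2, CYP2D6 and CYP19A1, "we will explore the relationship between the severity of arthralgias and degree of benefit from therapy in each of the treatment groups". The next sentence relates baseline and change in cytokines "with 12 weeks of treatment and the degree of benefit from therapy in each of the treatment groups".

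Section 11.3c, two items earlier, reads: "Interaction tests between treatment and stratification variables will be conducted to explore whether these factors are predictive of average pain scores". The closing paragraph of 11.3 gives the general model for linear scales as "multiple linear regression analyses including the baseline score as a covariate and the pre-specified stratification factors". Neither mentions the markers.

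**The concern.** A marker predicts response to duloxetine if the duloxetine-placebo difference varies with it. That is a statement about two arms. Within one arm, pain change also contains placebo response and natural course, so its association with a marker need not reflect benefit from duloxetine. In the placebo arm it cannot reflect that benefit at all. Two within-arm results, one significant and one not, are not a test that the arms differ.

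The distinction matters for these genes. Section 2.0 reports COMT variation associated with chronic and post-surgical pain in general, and aromatase variants that may predispose to AIMSS. Markers related to pain whatever the treatment are therefore a realistic case.

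At stake is how exploratory marker findings can be interpreted. The pilot had no control arm. This trial has one, and a direct contrast between arms is what it adds for this question.

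**Working it through.** **1. Aim against analysis.** Section 2.0 asks who responds to duloxetine, which calls for a marker-by-treatment contrast. Section 11.3e gives associations within each group. Section 11.3c gives treatment interactions, but only for baseline pain and prior taxane use. The general model in 11.3 has no marker term. The contrast is therefore not specified anywhere.

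**2. Inputs from Section 11.1.** The SD is 2.3, the diluted difference 0.85, two-sided alpha 0.05, and 115 patients per arm before the dropout allowance. Check: 2 × (1.960 + 0.842)² × 2.3² / 0.85² = 114.9, or 115 per arm, as stated. The plan gives no power or sample size for markers.

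**3. Assumptions not in the documents.** A binary marker with carrier share f; a true carrier difference d that is the same in both arms, so the true interaction is zero; and a reader who calls a marker predictive when it is significant on duloxetine and not on placebo.

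**4. Formulas.**
- Within-arm SE = 2.3 × √(1/(115f) + 1/(115(1−f)))
- Per-arm power p = Φ(d/SE − 1.96) + Φ(−d/SE − 1.96)
- P(significant on duloxetine only) = p(1−p), since the arms are independent
- Interaction SE = √2 × within-arm SE

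**5. Chance of misreading.**

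| d (points) | f | SE | p | p(1−p) |
|---|---|---|---|---|
| 0 | any | – | 0.05 | 0.048 |
| 0.3 | 25% | 0.495 | 0.09 | about 0.08 |
| 0.3 | 50% | 0.429 | 0.11 | about 0.10 |
| 0.85 | 10% | 0.715 | 0.22 | 0.17 |
| 0.85 | 25% | 0.495 | 0.40 | 0.24 |
| 0.85 | 50% | 0.429 | 0.51 | 0.25 |
| 1.5 | 50% | 0.429 | 0.94 | 0.06 |

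The maximum is 0.5 × 0.5 = 0.25. The probability falls again once the association is strong enough to show in both arms.

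**6. Interaction test on the same markers.** The nominal false-positive rate is 5% per marker. In 20,000 simulated trials with d = 0.85 it was 0.050 (50% carriers) and 0.051 (25%).

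**7. Cost in precision.** The interaction SE is 0.607, 0.700 or 1.011 at 50%, 25% or 10% carriers. Power for a 0.85-point interaction is 0.29, 0.23 or 0.13. The interaction detectable with 80% power (2.80 × SE) is 1.7, 2.0 or 2.8 points, against 1.2, 1.4 or 2.0 for a within-arm association.

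**8. Multiplicity.** Counting one independent null test for each of the seven genes, the chance of at least one false positive is 1 − 0.95⁷ = 0.30, before any cytokine is counted.

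**The case against.** The strongest reply is that 11.3e is under-specified rather than wrong. Objective k asks only for association with change in pain. Section 2.0 also has mechanistic aims, and severity of arthralgias is an outcome in 11.3e; for these, an association unrelated to duloxetine is a legitimate result. The work is labelled exploratory. All of this stands. It means the within-arm analyses should be kept, with the contrast added beside them.

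A reader might infer three stronger things that the documents do not support.
- *The placebo arm is ignored.* It is not: 11.3e examines the markers in both groups.
- *General pain markers will be reported as predictors of duloxetine response.* No section sets a rule for calling a marker predictive, and none says that significance on duloxetine alone would count.
- *The trial cannot answer the predictive question.* It can address it, with limited power. Patients are randomised, and Sections 5.3 and 15.1 require baseline whole blood and serum from all of them. The gap is in the stated analysis only.

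It is also fair that the 17–25% figures assume an association of 0.85 points, as large as the diluted treatment effect. Smaller associations give smaller figures, and with no association separate tests do no worse than an interaction test.

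Low interaction power is a true limit. It argues for reporting the interaction with its interval; comparing two p-values would hide the same uncertainty.

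**Conclusion.** The point holds as a gap in specification. Section 2.0 names prediction of duloxetine response as a purpose, and 11.3e provides no analysis that addresses it, although 11.3c uses the suitable method for other factors.

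The size is conditional. Under the assumed reading rule, a marker with equal association in both arms would be misread with probability of about 5% (no association), 8–10% (0.3 points, 25–50% carriers) and at most 25% (per-arm power 0.5), against 5% per marker for an interaction test. The rule, the marker effect and the carrier share are not in the documents. SD 2.3 and 115 per arm are borrowed from the primary design.

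Cytokine change is a separate matter. It is measured after treatment starts, so it cannot select patients beforehand, and an interaction term would not make it a pre-treatment predictor.

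The consequence is limited to the interpretation of exploratory findings. The primary and main secondary results are unaffected, and this is a minor point.

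**What to change.** In 11.3e:

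- For each gene variant and each baseline cytokine, fit one model over both arms for Week 12 BPI average pain, with arm, marker, arm-by-marker, baseline pain and the stratification factors. Report the interaction with its confidence interval as the exploratory evidence on prediction.
- Keep the within-arm associations as descriptive results for objective k and the mechanistic aims.
- For cytokine change, add the between-arm comparison that objective l calls for. Present change against benefit descriptively, not as a pre-treatment predictor.
- State how many markers are tested and that the results are hypothesis-generating.

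The cost is SAP wording and one model term per marker; no new data are needed. The downsides are wide interaction intervals and multiplicity across seven genes plus the cytokines, which the interaction test does not resolve by itself.
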